## FLOW CHART IV (MULTIPLE RISING DOSE PART, COHORT 3)

Trial Periods	Screening Period	Treatment Period						Follow-up Period			End of Trial 	
		1	2	2a 	3	3a 	4	4a 	5	6		
Visit											8	
Study Day	-14	1	2		29	30	57	58	85	113	141	169
Study Week					Week 4		Week 8		Week 12	Week 16	Week 20	Week 24
Time window for visits (days)	±10	none	+6	±3	+6	±3	+6	±3	±3	±3	±3	
Informed consent	X											
Demographics	X											
Medical history	X											
Physical examination 	X								X			
Vital signs	X	X		X		X			X	X	X	X
Laboratory tests	X	X		X		X			X	X	X	X
12 lead-ECG 	X	X		X		X			X			
Fluorescein angiography 	X											
Review of in-/exclusion crit.	X	X										
Dose Assignment		X										
IVT drug administration		X		X		X						
PK sampling		X		X		X			X	X	X	X
Biomarker sampling		X		X		X			X	X	X	X
ADA sampling		X		X		X			X			X
Biobanking		X 										
Visual Acuity testing	X	X		X		X			X	X	X	X
SD-OCT	X	X		X		X			X	X	X	X
OCT Angiography	X	X		X		X			X	X	X	X
Fundus Photo (multi-field) 	X	X	X	X	X	X	X	X	X	X	X	X
Fundus Photo (widefield)	X	X	X	X	X	X	X	X	X	X	X	X
Slit lamp	X	X	X	X	X	X	X	X	X	X	X	X
IOP	X	X		X		X			X	X	X	X
Adverse events	X	X	X	X	X	X	X	X	X	X	X	X
Concomitant therapy	X	X	X	X	X	X	X	X	X	X	X	X
Completion of patient participation 												X

(1) Completion of patient participation also needs to be completed if the patient withdraws prematurely following assignment to dose level (see [Section 3.3.4](#)).

(2) See [Section 5.2.6](#); the ECGs are to be recorded shortly before the PK sampling at the respective time points; see [Appendix 10.1](#).

Proprietary confidential information © 2022 Boehringer Ingelheim International GmbH or one or more of its affiliated companies

- (3) Collection of biobanking samples is optional. Participating patients are required to give informed consent specifically for biobanking. Samples will be stored at a biobanking facility for future research. DNA biobanking requires only one blood sample to be taken, preferably at Visit 2. However, collection at later visits is permitted as long as the informed consent for biobanking remains valid.
- (4) Vitreous haze assessment to be completed with every examination.
- (5) Physical examinations will also include measurement of weight and height (height only at Visit 1).

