For a more detailed description of the drug profile please refer to the current Investigator's Brochure (IB) [[c21397543](#)]. At the time of data cut-off for the current IB (25 March 2022), the SRD part of the trial described here (1336-0007) was completed: 15 patients had been treated with a single dose of intravitreal BI 836880 and followed up until the end of trial visit (EOT). In the ongoing MRD part, 14 patients had received at least one dose of BI 836880 ([Table 1.2: 1](#)). Six patients in the SRD part and 10 patients in the MRD part were reported with an adverse event (AE) after trial drug administration.

[figure not shown]
[figure not shown]
Table 1.2: 1 Summary of patient exposure to BI 836880\*

Trial part/cohort	1 dose	2 doses	3 doses	Total patients exposed per cohort
SRD	15	---	---	15
MRD/cohort 1		2	8	10
MRD/cohort 2	1	2	1	4

\* At the time of data cut off for the current IB (25 March 2022)

In the SRD part, all of the corresponding 6 AEs were eye disorders (conjunctival haemorrhage in the study eye, subretinal fluid in the study eye, dry eye in the study eye, 2 vitreous floaters in the study eye, neovascular AMD in the fellow eye). None of the reported AEs was judged as related to BI 836880 by investigators or fulfilled criteria for dose-limiting events. The AEs of neovascular AMD and of subretinal fluid were reported as of moderate intensity, the other AEs were rated as mild. The AE of neovascular AMD in the fellow eye was considered serious. All AEs but the neovascular AMD, the subretinal fluid and the dry

eye were recovered by the end of follow up.

[figure not shown]

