The SMC recommends the size for the next dose escalation cohort. After all patients in a cohort have either experienced an ocular DLE or have been observed for at least the 7 days evaluation period without experiencing a DLE, the Bayesian model will be updated with the newly accumulated data. The overdose risk will then be calculated for each dose, and escalation will be permitted to all planned doses which fulfil the EWOC criterion and the respective escalation rule. As a sensitivity analysis, the BLRM might also be run again shortly before the SMC meeting, using all data available up to this time point. Based on the model results and on additional information (PK, pharmacodynamics [PD], patient profiles), the members of the SMC will reach a joint decision on the next dose level to be investigated.

If DLEs are observed in the first two consecutive patients of a previously untested dose level, subsequent enrolment to that cohort will be stopped. The BLRM will be re-run to confirm that the dose level still fulfils the EWOC principle. Based on this information, the SMC will evaluate whether the next patients will be enrolled at the same dose level, or if they will be enrolled at a lower dose level.

The SMC may decide on stopping the dose escalation after the above criterion for MTD is fulfilled. Further patients may be included to confirm that the EWOC criterion is still fulfilled.

MRD part:

The MRD part will consist of a first part (1 mg) with 11 treatment-resistant patients (cohort 1), a second part (2 mg) with 4 treatment-naïve patients (cohort 2), and approximately 12 frequently treated patients (cohort 3; inclusion criteria defined in [Section 3.3.2](#)). These are the two highest doses established by the SMC as safe and tolerable during the SRD part. Patients that had received a dose in the SRD part of the trial will not be included. In the MRD

Proprietary confidential information © 2022 Boehringer Ingelheim International GmbH or one or more of its affiliated companies

groups, patients will receive three consecutive doses over a 3-month period (once a month dosing, [Figure 3.1: 2](#)). The SMC will decide on dose escalation after 3 patients from the first MRD cohort have completed visit 5 (first follow up visit). In all patients included in the MRD parts of the trial, safety and efficacy will be studied to 12 weeks after the treatment period.

[figure not shown]

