## 7.2 NULL AND ALTERNATIVE HYPOTHESES

There are no hypotheses tested in this exploratory trial.

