Description of change	
Revision and clarification of patients entered, cohort sizes, and dose groups in MRD part.
 
For number of patients entered (synopsis): ‘Approximately Up to 42; 15 in the SRD part and approximately up to 27 in the MRD part’
 
For number of patients on each treatment (synopsis): ‘SRD part: 15, in different dose groups MRD part: 11 10 to 12 patients in dose group 1 (=MRD cohort 1); approximately 16 10 to 17 patients in dose group 2, (4 patients from MRD cohort 2, 12 patients from cohort 3).’
 
For Section 3.1: ‘The MRD part will consist of a first <del>parteehort</del> (1 mg) with 1110 to 12 treatment-resistant patients <del>and</del>(cohort 1), a second <del>parteehort</del> (2 mg) with 410 to 17 treatment-naïve patients (cohort 2), and approximately 12 frequently treated patients (cohort 3; inclusion criteria defined in Section 3.3.2).’, amendment of n numbers and layout of Figure 3.1: 2
 
For Section 7.7: ‘To allow for dropouts, 10 to 12 patients will be included in MRD cohort 1 and approximately 16 10 to 17 patients will be included in MRD cohort 2 and 3 combined (in total approximately not more than 42 patients in the trial). In case some subjects do not complete the trial according to the protocol, the trial clinical monitor together with the trial pharmacokineticist and the trial statistician are to decide if and how many subjects will be replaced.’ and ‘For the MRD cohort 3, no formal sample size calculation has been applied. It is expected that using

	approximately 12 patients will be sufficient for this cohort.
Rationale for change	No change of total number of patients. Added the word “approximately” to account for potential variability in number of patients entered and number of patients that are randomized. Reiterated replacement strategy. Patients on each treatment adapted with results from completed SRD and MRD cohorts 1 and 2, 12 patients allocated to cohort 3. Clarification and addition of MRD cohort 3 patients to text in Section 3.1 and Figure 3.1: 2.
Section to be changed	Clinical Trial Protocol Synopsis: Diagnosis
Description of change	Addition of: ‘patients within 3 years of initial wAMD diagnosis for MRD cohort 3.’
Rationale for change	Additional requirement of patient population for MRD cohort 3
Section to be changed	Clinical Trial Protocol Synopsis: Main in- and exclusion criteria

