	
Visit 5), SoC therapy is at the discretion of the investigator. SoC therapy is, for the purpose of the present trial, considered a non-investigational medical treatment.
 
MRD cohort 3: For the study eye, no other treatment (IVT or otherwise) is allowed during the treatment and follow up periods of the trial unless rescue criteria are met (refer to Section 5.2.2 for rescue treatment criteria), or as deemed medically appropriate during/after Visit 6. Medications listed under the exclusion criteria (Section 3.3.3) are restricted during the trial. SoC therapy is, for the purpose of the present trial, considered a non-investigational medical treatment.'
 
Added to 5.2.2: 'The decision to treat with wAMD rescue medication should be documented in the eCRF.'
 
6.2.2.2 Amended: 'The investigator may decide to administer standard treatment for wAMD during the follow-up period (for MRD cohort 3 during/after Visit 6) as deemed medically appropriate.'

Rationale for change	Clarification that SoC therapy should be administered and documented if there is a worsening in disease before Visit 6, and as deemed medically appropriate during/after Visit 6.
Section to be changed	5.2.1 Dose limiting event; 5.2.8.1.4 Adverse events of special interest
Description of change	
Added to 5.2.1: Heading to SRD and MRD cohort 1 criteria and 'DLE criteria are not applicable to MRD cohorts 2 and 3. Should an event involving intraocular inflammation/signs of vascular occlusion, decreases in visual acuity, and/or intraocular pressure occur, the event should only be reported as an AESI as described in Section 5.2.8.1, and not as a DLE.'
 
Added to 5.2.8.1.4: detailed AESI criteria for ocular related events (intraocular inflammation, signs of retinal vascular occlusion, decreases in visual acuity, and intraocular pressure). Added NEI grading scale of vitreous haze (Table 5.2.8.1.4: 1)

Rationale for change	Clarification, additional AESI criteria described for cohorts receiving maximum dose (MRD cohorts 2 & 3)

Section to be changed	5.2.3 Physical examination

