7.8.1 Adverse Events

AEs will be coded with the most recent version of MedDRA. The version to be used will be specified in RPM and will be displayed as a footnote in the respective output.

The analyses of AEs will be descriptive in nature and will be based on BI standards as presented in “Analysis and Presentation of Adverse Event Data from Clinical Trials – Display Template” [BI-KMED-BDS-HTG-0041] (7) and [BI-KMED-BDS-HTG-0066] (2).

All analyses of AEs will be based on the number of subjects with AEs and not on the number of AEs.

The analysis of AEs will be based on the concept of treatment emergent AEs. That means that all AEs occurring between start of treatment and the EOT visit will be assigned to the respective treatment. All AEs occurring before first drug intake will be assigned to ‘screening’. For details on the treatment definition, see [Section 6.1](#).

Section 5.2.8.1.4 of the CTP:

All AEs meeting the criteria for a dose limiting event as defined in Section 7.4.1 are defined as AESIs for SRD and MRD cohort 1.

For MRD cohorts 2 and 3, the AESIs are defined as following:

Ocular related events (applicable to MRD cohorts 2 & 3)

- *Intraocular inflammation events*
 - *Anterior chamber cells of grade 1+ according to the Standardization of Uveitis Nomenclature (SUN) working group (WG) grading scheme (see CTP Table 5.2.1: I)*

- *Sterile inflammation of the vitreous of 1+ according to the NEI Grading of vitreous haze (see CTP Table 5.2.8.1.4: 1)*
- *Signs of vascular occlusion and inflammation (vasculitis) in the retina, including peripheral retinal hemorrhages in the area supplied by the occluded vessel (hemorrhage of the macula would not be included as this is a sign of wAMD disease)*
- *Visual acuity decrease of more than 15 letters from the previous visit*
- *Persistent IOP over 30 mmHg for 3 days after study treatment is administered, despite rescue treatment*

Hepatic injury

A hepatic injury is defined by the following alterations of hepatic laboratory parameters:

- *an elevation of AST and/or ALT ≥ 3 -fold ULN combined with an elevation of total bilirubin ≥ 2 -fold ULN measured in the same blood draw sample, and/or*
- *aminotransferase (ALT, and/or AST) elevations ≥ 10 -fold ULN*

These lab findings constitute a hepatic injury alert and the patients showing these lab abnormalities need to be followed up according to the “DILI checklist” provided in the eDC system.

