In case of clinical symptoms of hepatic injury (icterus, unexplained encephalopathy, unexplained coagulopathy, right upper quadrant abdominal pain, etc.) without lab results (ALT, AST, total bilirubin) available, the investigator should make sure these parameters are analysed, if necessary, in an unscheduled blood test. Should the results meet the criteria of hepatic injury alert, the procedures described in the DILI checklist should be followed.

According to ICH E3 ([15](#)), in addition to Deaths and serious adverse events, AEs classified as ‘other significant’ need to be listed in the clinical trial report. These will be any non-serious adverse event that led to an action taken with study drug (e.g., discontinuation or dose reduced or interrupted).

An overall summary of AEs (including number of patients with any AE, DLEs (applicable for SRD part and MRD part cohort 1 only), drug related AEs, procedure related AEs, ocular AEs, AESIs, serious AEs and drug related serious AEs) will be presented.

The frequency of patients with AEs will be summarized by treatment group/cohort, primary system organ class (SOC) and preferred term (PT). Separate tables will be provided for patients with ocular AEs, for patients with DLEs, for patients with serious AEs, for patients with drug-related AEs, for patients with drug-related serious adverse events, for patients with AESIs, for patients with drug-related AESIs and for patients with study procedure related AEs. In addition, the frequency of patients with AEs will be summarized by worst intensity, treatment group/cohort, SOC and PT.

The system organ classes will be sorted alphabetically, PTs will be sorted by frequency (within SOC).

In addition, frequencies of patients with non-serious AEs that have an incidence of $> 5\%$ for at least one treatment will be summarised by treatment, primary SOC and PT (both trial parts combined).

For disclosure of adverse events on EudraCT the following three entries will be created, combined for both trial parts:

- Adverse Events per arm for disclosure on EudraCT
- Non-serious Adverse Events for disclosure on EudraCT
- Serious Adverse Events for disclosure on EudraCT

For all ocular adverse events, ocular symptoms will be listed in addition.

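### SAP 7.8.1 applies to MRD cohort 2 an ocular AESI list introduced after that cohort's last scheduled visit, so its AESI count is not like-for-like with cohort 3 and may be an under-count

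*SAP*

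**What the plan says.** SAP 7.8.1 introduces the ocular list with "For MRD cohorts 2 and 3, the AESIs are defined as following". It has four categories: intraocular inflammation (anterior chamber cells at SUN grade 1+, or vitreous haze at NEI grade 1+), retinal vascular occlusion and vasculitis, a loss of more than 15 letters since the previous visit, and persistently raised IOP. The section plans tables of patients with AESIs and with drug-related AESIs by treatment group/cohort, and SAP 6.1 adds a total. The overall AE summary includes "DLEs (applicable for SRD part and MRD part cohort 1 only".

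Protocol 5.2.8.1.4 carries the same list. Protocol 11.7 shows that it came with Global Amendment 7, with the rationale "additional AESI criteria described for cohorts receiving maximum dose (MRD cohorts 2 & 3". Explaining the revised patient numbers, the same amendment states: "Patients on each treatment adapted with results from completed SRD and MRD cohorts 1 and 2".

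Protocol 3.1 describes "a second part (2 mg) with 4 treatment-naïve patients (cohort 2". Protocol 1.2 reports the position at the 25 March 2022 cut-off: "In the ongoing MRD part, 14 patients had received at least one dose of BI 836880".

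Routine haze grading appears only in Flow Chart IV (cohort 3), footnote 4: "Vitreous haze assessment to be completed with every examination". Flow Chart III (cohort 2) has no such requirement.

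The SAP does not say whether cohort 2 AESIs are flags that investigators set at the time or are derived afterwards. It does not mention when the definition was introduced.

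**The concern.** An AESI count depends on what investigators were told to report while patients were under observation. If the list did not yet exist, an absence of AESIs in cohort 2 does not mean the same as an absence in cohort 3. The two cohorts receive the same dose and stand side by side in the tables, so readers will compare them. Protocol 1.4 presents early detection of intraocular inflammation as a purpose of the added safety measures, and inflammation is where the old and new criteria differ most.

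There is also a gap on the DLE side. SAP 7.8.1 limits both the DLE entry and the DLE-based AESIs to the SRD part and cohort 1. A cohort 2 event recorded as a DLE at the time could drop out of both displays unless it also fits the newer AESI wording.

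**Working it through.** **1. Timing.** Inputs: Table 1.2: 1 (Protocol 1.2), Flow Chart III and Table 10.1: 2 (Day 169 ± 3), and Protocol 11.7 (28 Sep 2022, to be implemented only after approval).

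- Cohort 2 dosed by the cut-off: 1 + 2 + 1 = 4. This reproduces the table total and equals the cohort's final size. MRD total: 10 + 4 = 14, as stated.
- Scheduled end of trial: Day 1 + 6 × 28 = Day 169, as stated, which is 168 days after the first dose.
- The latest possible first dose is 25 Mar 2022. Adding 168 days gives 9 Sep 2022. Adding 171 (the +3-day window) gives 12 Sep 2022, 16 days before the amendment date.
- If all six later visits each slipped by 3 days and the slips accumulated, 168 + 6 × 3 = 186 days gives 27 Sep 2022, still 1 day before.

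The amendment's own description of cohort 2 as completed agrees with this.

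**2. What cohort 2 investigators could already report.** The heading limiting DLE criteria to the SRD part and cohort 1 was itself added by Amendment 7. Protocol 5.2.8.1.4 makes AEs that meet DLE criteria AESIs throughout the trial, and the log does not list that sentence as new. The two sets of criteria compare as follows.

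| Ocular AESI limb (Protocol 5.2.8.1.4) | DLE counterpart (Protocol 5.2.1) | Reportable in cohort 2 at the time? |
|---|---|---|
| Anterior chamber cells, SUN 1+ | Sterile endophthalmitis or vitreous inflammation, grade 4+, lasting 5 or more days | No, below the severe threshold |
| Vitreous haze, NEI 1+ | None on the NEI scale | No |
| Vascular occlusion and vasculitis, any retinal vessel | Occlusion of a 1st/2nd-degree vessel | In part |
| More than 15 letters lost since previous visit | More than 15 letters lost at any time point | Yes, wording differs |
| IOP over 30 mmHg for 3 days, despite rescue treatment | IOP over 30 mmHg for 3 days | Yes, wording differs |

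The two inflammation rows form one AESI category. Three of the four categories therefore had a full or partial counterpart; inflammation at grade 1+ did not.

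**3. What cohort 2 data exist.** Flow Chart III schedules slit lamp and AE collection at every visit, including 2a, 3a and 4a, and BCVA and IOP at every main visit. Fundus photography is unconditional only at screening and end of trial. SAP 7.9 tabulates SUN grade, BCVA and IOP by cohort. The anterior chamber and letter-loss limbs can therefore be derived. Persistence of raised IOP over 3 days cannot be programmed from readings about 4 weeks apart.

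**4. What a zero in cohort 2 would mean.** With complete ascertainment and an assumed true rate p, P(0 of 4) = (1 − p)^4: 0.81 at p = 5%, 0.66 at 10%, 0.32 at 25%. The exact two-sided 95% upper limit for 0/4 is 1 − 0.025^(1/4) = 60.2%. These rates are illustrative and do not come from the documents. A zero would be common even with full ascertainment.

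**5. Weight in the total.** The MRD total is 11 + 4 + 12 = 27, so cohort 2 is 4/27 = 14.8% of it.

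**The case against.** The strongest reply is that cohort 2 was examined closely. Slit lamp took place at every visit, all AEs were collected to end of trial, and the SAP already tabulates SUN grade, BCVA and IOP by cohort, lists vitreous cells and haze, and gives separate tables of ocular and drug-related AEs. AESIs are neither a primary nor a secondary endpoint, and Protocol 7.2 states: "There are no hypotheses tested in this exploratory trial". The SAP also defers data handling to a technical analysis data set plan, not among these documents, which may contain a derivation.

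Much of this stands, and it rules out three stronger readings.

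- A reader might infer that cohort 2 AESIs were never ascertained. The DLE criteria and the recorded examinations show otherwise for letter loss, IOP and larger-vessel occlusion.
- A reader might infer that the cohort 2 count is close to zero by construction. No document supports that, and 4 patients alone often give zero.
- A reader might infer that a pooled 2 mg proportion is diluted, with 16 patients in the denominator instead of 12. SAP 6.1 displays cohorts 2 and 3 separately and plans no such column; only the MRD total combines them.

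The reply does not remove the difference in definition for grade 1+ inflammation, vasculitis and haze, or the SAP's silence about it.

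**Conclusion.** The point holds for comparability. On the protocol schedule, no cohort 2 patient was under observation while the ocular AESI list was in force. Grade 1+ anterior chamber inflammation, vasculitis or occlusion beyond 1st/2nd-degree vessels, and NEI haze were not flagged prospectively in that cohort. The cohort 2 AESI count may be an under-count, should not be read against cohort 3 as it stands, and carries the same weakness into the MRD total. It concerns 4 patients in a descriptive table, and neither the direction nor the size of any error can be shown.

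Assumptions: no cohort 2 patient was added after the cut-off (4 dosed, final size 4); visits followed their windows; the DLE-based AESI rule predates Amendment 7; and no local amendment brought in the list earlier. Local amendments are mentioned, but none is said to have done so.

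**What to change.** In SAP 7.8.1:

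- For both cohorts 2 and 3, derive two limbs from recorded data: SUN anterior chamber grade 1+ or higher at any post-dose slit lamp, and a loss of more than 15 letters from the previous visit. Show them beside the investigator-reported AESIs.
- In cohort 2, identify IOP and vascular events by review of the recorded AEs, not by program.
- Show NEI vitreous haze as not systematically assessed for cohort 2 and leave those 4 patients out of that denominator.
- Footnote that the definition dates from Amendment 7 (28 Sep 2022).
- Reconcile three statements: SAP 7.8.1 (DLE-based AESIs for the SRD part and cohort 1 only), Protocol 5.2.8.1.4 (DLE-type events are AESIs throughout the trial) and Protocol 5.2.1 (DLE criteria not applicable to cohorts 2 and 3). Any event recorded as a DLE while cohort 2 was on study should still be reported. Simply restoring a DLE row for cohort 2 would conflict with Protocol 5.2.1.

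The cost is SAP wording, a small amount of programming and an AE review for 4 patients. No new data are needed.
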